6.3.3 Cabozantinib

The most frequent AEs experienced by $\geq 20\%$ of subjects treated with cabozantinib in descending order of frequency were diarrhea, fatigue, decreased appetite, nausea, weight decreased, PPES, vomiting, constipation, hypertension, dysgeusia, dysphonia, asthenia, and dyspnea. For a full description of the safety profile of cabozantinib, refer to the Cabozantinib Investigator's Brochure.

Other medically important but less frequent AEs including arterial thrombotic AEs (eg, transient ischemic attack [TIA], and myocardial infarction [MI]) and venous thrombotic AEs (eg, deep vein thrombosis [DVT] and pulmonary embolism), severe hemorrhagic events, proteinuria, wound healing complications, gastrointestinal (GI) perforation, abscesses including intra-abdominal and pelvic abscess, GI and non-GI fistula formation, osteonecrosis, and reversible posterior leukoencephalopathy syndrome (RPLS).

Adverse events associated with laboratory abnormalities experienced by $\geq 5\%$ of subjects treated with cabozantinib in descending order of frequency were anemia, AST increased, ALT increased, hypothyroidism, hypokalemia, hypomagnesemia, thrombocytopenia, hypocalcemia, hypophosphatemia, lactate dehydrogenase (LDH) increased, lipase increased, neutropenia, hyponatremia, ALP increased, leukopenia, and hyperglycemia.

Adverse events may occur within the first few weeks in the course of treatment with cabozantinib, as cabozantinib is expected to reach steady state exposure at approximately 2 weeks following first dose. Events that generally have an early onset include hypocalcemia, hypokalemia, thrombocytopenia, hypertension, PPES, abdominal pain, mucosal inflammation, constipation, diarrhea, and vomiting. Adverse events should be managed with supportive care at the earliest signs of toxicity. Dose reductions and treatment interruptions should be considered. Dose reductions are recommended for events that, if persistent, could become serious or intolerable (Section 6.3).

Cabozantinib should be discontinued for the following AEs: visceral perforation or fistula formation, severe hemorrhage, serious arterial thromboembolic events, nephrotic syndrome, hypertensive emergency, persistent uncontrolled hypertension despite optimal medical management, and RPLS.

6.3.3.1 Gastrointestinal Disorders

Gastrointestinal perforation, GI fistula, and intra-abdominal and pelvic abscess: After starting treatment with cabozantinib, subjects should be monitored for early signs of GI perforation such as abdominal pain, nausea, emesis, constipation, and fever especially if known risk factors for developing GI perforation or fistula (Turnage and Badgwell 2016) are present. Discontinue cabozantinib and initiate appropriate management in subjects who have been diagnosed with GI perforation or fistula.

Diarrhea: Subjects should be instructed to notify their physician or other study team member immediately at the first signs of poorly formed or loose stool or an increased frequency of bowel movements. Guidelines for the evaluation and management of diarrhea are shown in Table 6-4. Administration of antidiarrheal/antimotility agents is recommended at the first sign of diarrhea as initial management. Some subjects may require concomitant treatment with more than one antidiarrheal agent. When therapy with antidiarrheal agents does not control the diarrhea to tolerable levels, cabozantinib should be temporarily interrupted or dose reduced. When the diarrhea is controlled, retreatment with cabozantinib may be acceptable per investigator decision. In addition, general supportive measures should be implemented such as continuous oral isotonic hydration, correction of fluid and electrolyte abnormalities, small frequent meals, and stopping lactose-containing products, high-fat meals, and alcohol.

Recurrent or prolonged diarrhea can be associated with anal or perianal skin erosions which increase the risk for anal abscesses, fistulas, or proctitis. Good personal hygiene should be emphasized. Regular examinations of the perianal region should be performed whenever diarrhea has occurred during treatment with cabozantinib. Infections of the perianal region should be treated per local guidelines.

Table 6-4: Management of Diarrhea Associated with Cabozantinib

Status	Management
Tolerable Grade 1-2 (duration < 48 h)	
 • Continue with study treatment and consider dose reduction • Initiate treatment with an antidiarrheal agent (eg, loperamide 4 mg followed by 2 mg after each episode of diarrhea [maximum: 16 mg loperamide per day]) • Dietary modifications (eg, small lactose-free meals, bananas and rice) • Intake of isotonic fluids (1-1.5 L/day) • Re-assess after 24 hours: 
 ○ Diarrhea resolving to baseline bowel habits: gradually add solid foods and discontinue or decrease antidiarrheal treatment after 12 h diarrhea-free interval ○ Diarrhea not resolving: Continue/resume antidiarrheal treatment
Intolerable Grade 2, Grade 2 > 48 h, or ≥ Grade 3	
 • Interrupt study treatment • Ask subject to attend clinic • Rule out infection (eg, stool sample for culture) 
 ○ Administer antibiotics as needed (eg, if fever or Grade 3-4 neutropenia persists > 24 h) • Administer fluids (1-1.5 L/day orally or IV, as appropriate) for hydration or to correct electrolyte abnormalities • For Grade 3-4 or complicated lower grade diarrhea consider hospitalization and IV hydration • Re-assess after 24 h 
 ○ Diarrhea resolving to baseline bowel habits or Grade ≤ 1: consider restarting study treatment at reduced dose ○ Diarrhea not resolving: Start and or continue antidiarrheal treatment (eg, loperamide 4 mg followed by 2 mg after each episode of diarrhea [maximum: 16 mg loperamide per day]). Consider starting second line antidiarrheal or referral to gastroenterologist

Nausea and vomiting: Antiemetic agents are recommended as clinically appropriate for treatment or prophylaxis of nausea and vomiting, along with supportive care. Dehydration and electrolyte abnormalities may be associated with vomiting and monitoring for and correction of fluid and electrolyte disturbances should be implemented. Antiemetic medications should be assessed for potential drug interactions (refer to Section 7.3 for further details).

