6.3 Cabozantinib Dose Modifications, Interruptions, and Discontinuation

The following should be taken into consideration in decisions regarding dose modifications (reductions or interruption):

- As a general approach all AEs should be managed with supportive care at the earliest signs of toxicity considered related to the study treatment. Should this be ineffective, dose interruptions and/or reductions should be considered to prevent worsening of toxicity.
- The assigned starting dose for cabozantinib is 60 mg/day. 2 dose reduction levels of cabozantinib are permitted (see Table 6-2).
- Dose modification criteria for cabozantinib are shown in Table 6-3. Dose interruptions and/or reductions should be implemented for unacceptable toxicity. Doses may be modified at any time while a subject is on treatment.
- Dose reductions or interruptions may also occur in the setting of lower grade toxicity than defined in Table 6-3, if the investigator feels it is in the interest of a subject’s safety and will optimize drug tolerability.
- Interruption of cabozantinib treatment for cabozantinib-related AEs may occur at any time per investigator discretion. If treatment is interrupted due to related AEs for more than 6 weeks, cabozantinib should be discontinued unless there is unequivocal evidence that the subject is benefitting. In this situation, a subject may be able to restart therapy with a dose reduction upon resolution of the toxicity per the discretion of the investigator.
- Dose interruptions for reason(s) other than related AEs (eg, surgical procedures) can be longer than 6 weeks per the discretion of the investigator.

Guidelines for the management of specific AEs are provided in Section 6.3.3.

Table 6-2: Dose Reductions of Cabozantinib

Assigned Dose	First Dose Level Reduction	Second Dose Level Reduction
60-mg cabozantinib oral qd	40-mg cabozantinib oral qd	20-mg cabozantinib oral qd
40-mg cabozantinib oral qd	20-mg cabozantinib oral qd	No dose reduction permitted
20-mg cabozantinib oral qd	No dose reduction permitted	—

qd, once daily

Cabozantinib will be discontinued if a qd dose of 20-mg cabozantinib (minimum dose) is not tolerated

Table 6-3: Dose Modifications of Cabozantinib for Treatment-Related AEs

CTCAE v.4.0 Grade	Recommended Guidelines for Management ^a
Grade 1 AEs	Add supportive care as indicated. Continue cabozantinib treatment at the current dose level if AE is manageable and tolerable.

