Grade 2 AEs which are tolerable and are easily managed	Continue cabozantinib treatment at the current dose level with supportive care.
Grade 2 AEs which are intolerable and cannot be adequately managed	At the discretion of the investigator, cabozantinib should be dose reduced or interrupted. Note: It is recommended that dose holds be as brief as possible.
Grade 3 AEs (except clinically non-relevant laboratory abnormalities)	Cabozantinib should be interrupted unless the toxicity can be easily managed with a dose reduction and optimal medical care. Note: It is recommended that dose holds be as brief as possible.
Grade 4 AEs (except clinically non-relevant laboratory abnormalities)	Subjects should have cabozantinib interrupted immediately. Discontinue cabozantinib unless the following criteria are met: 
 • Subject is deriving clear clinical benefit as determined by the investigator • Toxicity can be managed with a dose reduction following recovery to Grade 1 (or baseline) and optimal medical care

AE, adverse event.

Note: The dose delay and modification criteria for specific medical conditions are provided in Section 6.3.2. For re-treatment criteria of study treatment after a dose hold see Section 6.3.1.

^a Study treatment dose adjustment is only needed if the toxicity was deemed related to cabozantinib treatment or had an unclear relationship to cabozantinib treatment.

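### Diarrhea dosing rules disagree: for tolerable, easily managed Grade 2 lasting over 48 h, Table 6-3 continues and Table 6-4 interrupts, and no text says which governs

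*Combined protocol and SAP*

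**What the plan says.** Three places in the protocol bear on dosing during diarrhea.

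- **Table 6-3 (Section 6.3), all treatment-related events.** Grade 1: "Continue cabozantinib treatment at the current dose level if AE is manageable and tolerable". For "Grade 2 AEs which are tolerable and are easily managed" the action is "Continue cabozantinib treatment at the current dose level with supportive care". For Grade 2 that is intolerable and cannot be adequately managed, the investigator may reduce or interrupt. None of these rows has a duration limit.
- **Section 6.3.3.1, text on diarrhea.** "When therapy with antidiarrheal agents does not control the diarrhea to tolerable levels, cabozantinib should be temporarily interrupted or dose reduced". This sentence turns on tolerability and does not mention duration. The same paragraph refers to Table 6-4 for management guidelines.
- **Table 6-4 (Section 6.3.3.1).** The first row is "Tolerable Grade 1-2 (duration < 48 h", with the dosing action "Continue with study treatment and consider dose reduction". The second row is "Intolerable Grade 2, Grade 2 > 48 h, or ≥ Grade 3", with the dosing action "Interrupt study treatment".

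Two pointers connect these places. The list in Section 6.3 sends sites to Section 6.3.3 for specific adverse events. The note under Table 6-3 sends them to Section 6.3.2 for criteria on specific conditions.

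**The concern.** A dosing rule should give one answer for one clinical state. Here a patient with tolerable, easily managed Grade 2 diarrhea on day 3 stays on the current dose under one table and is interrupted under another. Uncontrolled diarrhea has a dose-reduction option in two places and not in the third.

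The stakes lie in exposure and in the tolerability data. Treatment lasts 12 weeks, only the week-12 scan counts for the primary objective (Section 5.6), and safety and tolerability are a secondary objective (Section 2). The interruption branch can also outlast the pause. On recovery, Table 6-4 asks the site to consider restarting at a reduced dose, and Section 6.3.1 allows restart at a reduced dose after a possibly related toxicity. From 60 mg the next level in Table 6-2 is 40 mg, a cut of (60 − 40)/60 = 33%, although Section 6.3.1 leaves room for re-escalation. Two sites acting in good faith could therefore record different interruptions and reductions for the same patient, and those counts would partly reflect the reader rather than the drug.

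**Working it through.** The plan states no figure on this point, so the check is a comparison of texts. Each rule is applied to the same clinical state.

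**State A: Grade 2, tolerable and easily managed, more than 48 h.**
- Table 6-3: continue at the current dose. Both conditions of the row are met and it has no time limit.
- Section 6.3.3.1 text: its trigger, failure to reach a tolerable level, is not met. It is silent on what else should happen.
- Table 6-4: interrupt. The second row lists intolerable Grade 2 separately, so its item for Grade 2 over 48 h must take in tolerable Grade 2.
- Result: two opposing written instructions, plus one text that names no duration trigger.

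**State B: diarrhea not controlled to a tolerable level, including intolerable Grade 2.**
- Section 6.3.3.1 text: interrupt or reduce.
- Table 6-3, intolerable Grade 2 that cannot be adequately managed: reduce or interrupt.
- Table 6-4: interrupt. A reduced dose appears only later, at restart.
- Result: the reduction-without-interruption option exists in two places and is absent from the third. The text and Table 6-4 disagree here within one subsection.

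**State C: Grade 1, 48 h or more.**
- Table 6-4: no row. The first row stops short of 48 h and the second starts at Grade 2.
- Table 6-3: the general Grade 1 row applies, whatever the duration.
- Result: a gap in the diarrhea table, covered only by the general table. Tolerable Grade 2 at exactly 48 h also falls between the two rows of Table 6-4.

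**A softer difference.** For tolerable, easily managed Grade 2 under 48 h, Table 6-4 asks the site to consider a reduction while Table 6-3 keeps the current dose. The word *consider* makes this a difference of emphasis.

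**Routing.** Section 6.3 points to 6.3.3, where the diarrhea rules are. The Table 6-3 note points to 6.3.2, which covers adverse event monitoring and grading and has no diarrhea criteria. Neither pointer says which text prevails when they differ.

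**Size.** The input needed is the proportion of patients with tolerable Grade 2 diarrhea lasting more than 48 h, and the documents do not give it. Section 1 gives Grade 3 or 4 diarrhea of 13% and 10% on cabozantinib in two metastatic trials, which is a different event in a different setting. No estimate is made.

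**The case against.** The strongest reply is that the specific guidance is meant to prevail. Section 6.3 sends sites to 6.3.3 for specific events, the Section 6.3.3.1 text hands management of diarrhea to Table 6-4, and even the misdirected note tells the reader that specific conditions have their own criteria. Section 6.3.2 comes directly before 6.3.3, so a site would probably find the right page. Both tables are framed as guidelines. Section 6.3 also lets the investigator interrupt for related events at any time and act at lower grades than Table 6-3 lists, so no text forbids a hold.

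Much of this stands. The routing favors Table 6-4, and the easily-managed condition narrows State A, since Grade 2 diarrhea that persists on antidiarrheals may not meet it. But precedence is nowhere stated. The latitude covers a site that holds; it does not say whether a site may continue when Table 6-4 says interrupt. State B lies inside 6.3.3.1, so preferring specific over general guidance does not settle it.

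Four stronger readings are tempting and are not supported:

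- *Three different dosing rules for State A.* There are two outcomes. Continuing at the current dose and making no change are the same dosing.
- *The 6.3.3.1 text directs sites to continue when diarrhea is tolerable.* It gives one trigger for acting and does not call it the only one. No change is an inference from silence.
- *Persistent Grade 1 has no rule at all.* The Grade 1 row of Table 6-3 covers it.
- *The effect can be sized from the Grade 3 or 4 rates, or from a six-week hold.* Those rates do not measure the disputed state. Table 6-4 asks for re-assessment after 24 h; six weeks is the separate discontinuation limit in Section 6.3.

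**Conclusion.** The inconsistency is real and limited. For Grade 2 diarrhea that is tolerable, easily managed and lasts more than 48 h, Tables 6-3 and 6-4 give opposite instructions. For diarrhea not controlled to a tolerable level, Table 6-4 lacks the dose-reduction option that the text above it and Table 6-3 both allow. Table 6-4 leaves out Grade 1 of 48 h or more, one cross-reference is wrong, and nothing states precedence.

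The conclusion on State A assumes that some Grade 2 diarrhea over 48 h is still judged easily managed; where it is not, that conflict with Table 6-3 falls away and the State B mismatch remains. The effect on exposure, on counts of interruptions and reductions, or on week-12 response cannot be quantified from the documents, and none has been shown. The two-stage design and its decision rule are not touched. The point still merits correction because it concerns the first-listed adverse event and affects which dosing action a site takes.

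**What to change.** At the next amendment the sponsor and investigator should:

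- reconcile the Grade 1 and Grade 2 rows of Table 6-3, the diarrhea text of Section 6.3.3.1 and Table 6-4, so that each combination of grade, tolerability and duration has one action, including Grade 1 of 48 h or more and the 48 h boundary itself;
- make the text and Table 6-4 agree on whether dose reduction is an alternative to interruption;
- state in Section 6.3 which text governs if they differ;
- correct the note under Table 6-3 so that it and the list in Section 6.3 point to the same section.

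Which action applies, and which text governs, is for the sponsor and investigator to decide; no view is taken here. The cost is a wording change, with no added visits, patients or data.

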6.3.3.2 Non-Gastrointestinal Fistula

Complications from radiation therapy especially of the thoracic cavity including mediastinum have been identified as a possible predisposing risk factor for non-GI fistula formation in subjects undergoing treatment with VEGF pathway inhibitors.

Discontinue cabozantinib and initiate appropriate management in subjects who have been diagnosed with a non-GI fistula.

6.3.3.3 Hemorrhage

Hemorrhagic events, including serious and sometimes fatal events, have been reported with cabozantinib. Subjects should be monitored for bleeding events with serial complete blood counts and physical examination while on study. The risk of hemorrhage in cabozantinib-treated subjects with brain metastases has not been thoroughly analyzed. Subjects enrolled with treated and stable brain metastases should be monitored with a high index of suspicion if symptoms that could be due to a CNS hemorrhage occur.

Cabozantinib should be discontinued in subjects with serious and life-threatening bleeding events or recent hemoptysis (≥ 2.5 mL of red blood).

6.3.3.4 Thromboembolic events

Thromboembolic events are frequent in cancer subjects due to procoagulant changes induced by the malignancy or anticancer therapy. DVT and pulmonary embolism have been observed in clinical studies with cabozantinib, including fatal events. Subjects who develop a pulmonary embolism and/or DVT should have study treatment interrupted until therapeutic anticoagulation is established. Treatment with cabozantinib may be resumed in subjects with pulmonary embolism or DVT if it is determined that the event is uncomplicated and that the subject is deriving clinical benefit from cabozantinib treatment and that anticoagulation does not place them at a significant risk that outweighs the benefit of resuming treatment per discretion of the investigator and according to individual protocols. Low molecular weight heparins are the preferred management for thrombotic events; oral anticoagulants (eg, warfarin or other coumarin-related agents, direct thrombin or direct FXa inhibitors, or antiplatelet agents, or chronic use of aspirin above low dose levels for cardioprotection per local applicable guidelines) are not allowed.

Arterial thrombotic events (eg, TIA, MI) have been observed in studies with cabozantinib. Further treatment with cabozantinib should be discontinued in subjects who develop an acute MI, cerebral infarction, or any other clinically significant arterial thromboembolic complication.

6.3.3.5 Hypertension

Table 6-5 provides treatment guidelines for hypertension deemed related to cabozantinib. Blood pressure should be monitored in a constant position visit to visit, either sitting or supine in a relaxed setting. Decisions to reduce or interrupt the dose of study treatment must be based on BP readings taken by a medical professional and must be confirmed with a second measurement at least 5 minutes following the first measurement.

Cabozantinib should be discontinued in subjects with hypertensive emergency.

Table 6-5: Management of Hypertension Associated with Cabozantinib

Criteria for Dose Modifications	Treatment/Cabozantinib Dose Modification
Subjects NOT receiving optimized anti-hypertensive therapy	
> 150 mm Hg (systolic) ^a and < 160 mm Hg OR > 100 mm Hg (diastolic) and < 110 mm Hg	
 Optimize antihypertensive medications by adding new or additional antihypertensive medications and/or increase dose of existing medications. Reduce cabozantinib treatment by one dose level if optimal antihypertensive therapy (usually to include 3 agents) does not result in BP <150 mm Hg systolic or <100 mm Hg diastolic If subject is symptomatic interrupt cabozantinib treatment
≥ 160 mm Hg (systolic) OR ≥ 110 mm Hg (diastolic)	
 Reduce cabozantinib by one dose level^b or interrupt cabozantinib treatment per investigator discretion Add new or additional anti-hypertensive medications and/or increase dose of existing medications and monitor subject closely for hypotension. If optimized antihypertensive therapy (usually to include 3 agents) does not result in BP < 150 mm Hg systolic or < 100 mm Hg diastolic, cabozantinib treatment should be dose reduced further or interrupted Cabozantinib treatment should be dose interrupted if upper limits of systolic BP (≥ 160 mm Hg) are sustained and not adequately manageable or if systolic BP is > 180 mm Hg or diastolic BP > 110 mm Hg, or if subject is symptomatic Re-start cabozantinib treatment at the most tolerable dose and re-escalate only if BP falls to and is sustained at < 150 mm Hg systolic and < 100 mm Hg diastolic
Hypertensive emergency ^c	
 Discontinue cabozantinib treatment

BP, blood pressure.

^a The investigator may decide to initiate or adjust antihypertensive treatment at a lower threshold than systolic BP >150 or diastolic BP >100 based on their clinical judgment and assessment of the individual subject.

^b Permitted dose levels are defined by individual protocols.

^c Hypertensive emergency is defined as uncontrolled elevated BP with clinical evidence of progressive or impending end-organ damage (eg, myocardial infarction/ischemia, intracranial hemorrhage, cerebral ischemia, pulmonary edema, encephalopathy, kidney damage).

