4.2 Exclusion Criteria

1. Evidence of metastatic disease on pre-treatment imaging.
2. The subject has received of any type of cytotoxic, biologic or other systemic anticancer therapy for kidney cancer;
3. The subject has received any other type of investigational agent within 28 days before the first dose of study treatment;
4. Known brain metastases or cranial epidural disease.
5. Concomitant anticoagulation with oral anticoagulants (eg, warfarin, direct thrombin and Factor Xa inhibitors) or platelet inhibitors (eg, clopidogrel). Allowed anticoagulants are the following:
 - Low-dose aspirin for cardioprotection (per local applicable guidelines) is permitted.
 - Low-dose low molecular weight heparins (LMWH) are permitted.
 - Anticoagulation with therapeutic doses of LMWH is allowed in subjects without known brain metastases who are on a stable dose of LMWH for at least 6 weeks before first dose of study treatment, and who have had no clinically significant hemorrhagic complications from the anticoagulation regimen or the tumor.
6. The subject has prothrombin time (PT)/INR or partial thromboplastin time (PTT) test $\geq 1.3 \times$ the laboratory ULN within 14 days before the first dose of study treatment.
7. The subject has uncontrolled, significant intercurrent or recent illness including, but not limited to, the following conditions:
 - Cardiovascular disorders:

- Congestive heart failure New York Heart Association Class 3 or 4, unstable angina pectoris, serious cardiac arrhythmias.
- Uncontrolled hypertension defined as sustained blood pressure (BP) > 150 mm Hg systolic or > 100 mm Hg diastolic despite optimal antihypertensive treatment.
- Stroke (including transient ischemic attack [TIA]), myocardial infarction (MI), or other ischemic event, or thromboembolic event (eg, deep venous thrombosis, pulmonary embolism) within 6 months before first dose.
- Gastrointestinal (GI) disorders including those associated with a high risk of perforation or fistula formation:
 - The subject has evidence of tumor invading the GI tract, active peptic ulcer disease, active inflammatory bowel disease (eg, Crohn's disease), diverticulitis, cholecystitis, symptomatic cholangitis or appendicitis, acute pancreatitis, acute obstruction of the pancreatic duct or common bile duct, or gastric outlet obstruction.
 - Abdominal fistula, GI perforation, bowel obstruction, or intra-abdominal abscess within 6 months before first dose.

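### Table 6-5 joins the two blood-pressure limits with 'or', so in its first row an isolated raised systolic or diastolic pressure on optimized therapy triggers no stated dose reduction

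*Combined protocol and SAP*

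**What the plan says.** Table 6-5 has two rows of pressure thresholds under a sub-heading for subjects not yet on optimized antihypertensive therapy.

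- **First row, entry.** Systolic above 150 and below 160, or the diastolic equivalent: "< 160 mm Hg OR > 100 mm Hg (diastolic) and < 110 mm Hg". Either pressure alone qualifies.
- **First row, reduction.** After antihypertensives are optimized, cabozantinib goes down one level if that therapy "does not result in BP <150 mm Hg systolic or <100 mm Hg diastolic".
- **First row, only other change to cabozantinib.** "If subject is symptomatic interrupt cabozantinib treatment".
- **Second row, entry (systolic at least 160 or diastolic at least 110).** Reduce one level or interrupt at once, at the investigator's discretion.
- **Second row, further step.** If optimized therapy "does not result in BP < 150 mm Hg systolic or < 100 mm Hg diastolic, cabozantinib treatment should be dose reduced further" or interrupted.
- **Second row, interruption.** For systolic of 160 or more that is sustained and not adequately manageable, "or if systolic BP is > 180 mm Hg or diastolic BP > 110 mm Hg", or for symptoms.
- **Second row, going back up.** Re-escalation is allowed only if the pressure "is sustained at < 150 mm Hg systolic and < 100 mm Hg diastolic".

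Elsewhere, exclusion 7 in Section 4.2 defines uncontrolled hypertension as "sustained blood pressure (BP) > 150 mm Hg systolic or > 100 mm Hg diastolic despite optimal antihypertensive treatment". Section 6.3.3 lists "persistent uncontrolled hypertension despite optimal medical management" among the reasons to discontinue, without giving numbers. Section 6.3 lets the investigator reduce or interrupt at discretion.

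**The concern.** The two reduction bullets turn on failure to reach a target, and the target is stated as an alternative. A target of one limit *or* the other is missed only when both are missed. A subject whose systolic pressure stays at 155 on optimized therapy, with diastolic 95, has therefore met the target as written and stays at the same dose.

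The table sets an operative rule. Section 6.3.3.5 requires decisions to reduce or interrupt to rest on readings taken by a medical professional and confirmed by a second measurement. Hypertension is also a leading severe toxicity in the protocol's own background (Section 1): grade 3 or 4 in 15% of cabozantinib patients in the phase III second-line trial and 28% in the randomized first-line phase II trial. Those rates are context only. They do not say how often one pressure alone stays high on optimized therapy.

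**Working it through.** The plan gives no figure to reproduce here; the check is of the rule's logic. Let S be systolic and D diastolic pressure in mm Hg, on optimized therapy, with the subject asymptomatic.

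**Step 1. The trigger.**

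- As written: reduce if NOT(S < 150 or D < 100), which equals S ≥ 150 and D ≥ 100.
- With *and*: reduce if NOT(S < 150 and D < 100), which equals S ≥ 150 or D ≥ 100.

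The two versions differ exactly where one pressure, and only one, is at or above its limit.

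**Step 2. First-row values.**

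| S/D | Trigger as written | Trigger with *and* | Re-escalation target met | Above an exclusion 7 limit |
|---|---|---|---|---|
| 145/95 | no | no | yes | no |
| 155/95 | no | yes | no | yes |
| 145/105 | no | yes | no | yes |
| 155/105 | yes | yes | no | yes |

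The second and third lines show the conflict. Both patterns qualify for entry to the first row, fail the re-escalation target and, if sustained, count as uncontrolled under exclusion 7, yet neither triggers the reduction. A subject who enters the first row at 155/95 already meets the literal target before any antihypertensive is added, so for entries on a single pressure the bullet can never act unless the other pressure rises as well.

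**Step 3. What else in the table catches these values.**

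- *First row.* The only other change to cabozantinib is interruption for symptoms. Isolated S 150–159 (D < 100) and isolated D 100–109 (S < 150) meet no other numeric bullet.
- *Second row.* Entry on either pressure has already led to a reduction or interruption. After that, 165/95 is interrupted if sustained and not adequately manageable, and 145/112 is interrupted because D > 110. What neither the *or* bullet nor the interruption bullet catches is S 150–159 with D < 100, or D 100–110 with S < 150. A diastolic of exactly 110 still meets the row's entry criterion. Only a further step is missed here, not the first one.

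**Step 4. After the change.** With *and*, the trigger S ≥ 150 or D ≥ 100 is the exact complement of the re-escalation target (S < 150 and D < 100). No pair of values that fails the re-escalation target is left without a trigger.

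**The case against.** The strongest reply is that no sensible investigator would use the literal reading. Because the row is entered on either pressure, the *or* in the bullet can be taken to mirror the entry: whichever limit was exceeded was not brought back. That is probably what was meant. It still leaves one sentence that supports opposite actions for the same subject, and the literal sense is the less protective one.

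Second, the comparison texts are not all equally strong. Exclusion 7 is an eligibility threshold, and on-treatment limits need not match it. The *and* target follows the words on re-escalation, and a stricter test for raising the dose than for lowering it would be coherent. Both points are fair. The first row's own entry criterion carries the argument, since it admits subjects for whom the literal bullet can have no effect; the other two texts support it.

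Third, other provisions apply. Section 6.3 allows dose changes at any time and below the grades in Table 6-3. Table 6-3 itself provides for reduction or interruption of poorly managed Grade 2 events and, as a rule, interruption for Grade 3. Section 6.3.3.5 presents Table 6-5 as guidelines. These limit the practical risk, but discretion is permissive and does not repair the trigger, and Table 6-3 has no pressure limits and defers to condition-specific guidance.

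**Conclusion.** The concern holds as a minor wording error in safety conduct. As written, both bullets need both pressures at or above their limits. The consequence falls mainly on the first row: isolated systolic 150–159 or isolated diastolic 100–109 in an asymptomatic subject on optimized therapy. This rests on the literal reading of *or*; an investigator who reads it as either limit missed would act correctly.

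A reader might infer more, and the documents do not support it:

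- *That one uncontrolled pressure never leads to a reduction anywhere in the table.* The second row reduces or interrupts on either pressure at entry and interrupts again at higher values.
- *That the Section 6.3.3 stop rule is another contradiction.* It gives no numeric definition, so it neither confirms nor conflicts with the bullets. It is a backstop.
- *That a measurable share of subjects is at risk.* The documents give no count of subjects left with one raised pressure on optimized therapy, so no frequency can be stated.
- *That the primary result is affected.* Nothing here bears on the response rate or on the Simon decision.

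**What to change.** In both reduction bullets of Table 6-5, replace *or* with *and* between the two limits, so that the target is systolic below 150 mm Hg and diastolic below 100 mm Hg together. Make no other change: the entry criteria, the interruption and re-escalation bullets and the Section 6.3.3 stop rule can stand, and no new escalation step is needed in the first row.

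The cost is one word in each of two bullets at the next amendment, with no effect on sample size, visits or analysis.
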